5.4 Potential Pazopanib Specific Side Effects

- 5.4.1 Hypertension
 - **Baseline blood pressure** (BP) is defined as the blood pressure obtained at the examination used for study enrollment. This baseline BP should be obtained as follows:
 - 1) Obtain 3 serial blood pressures from the same extremity with the patient in the same position that are separated by at least 5 minutes. Avoid using the lower extremity if possible.
 - 2) Average the systolic blood pressure from the 2^{nd} and 3^{rd} measurements.
 - 3) Average the diastolic blood pressure from the 2^{nd} and 3^{rd} measurements.
 - 4) The baseline BP is the average of the systolic over the average of the diastolic measurements.
 - Elevation in either the systolic or diastolic blood pressure should be considered when following the algorithm below.
 - The upper limit of normal (ULN) is defined as a BP equal to the 95th percentile for age, height, and gender. If ≥ 18 yrs of age, ULN will be defined as a BP of 140/90. See Appendix V.
 - The NCI CTCAE version 4.0 will be utilized to determine the grade of hypertension for reporting purposes.
 - Elevated BP measurements should be repeated on the same day to confirm the elevation. Patients with an elevated BP should have BP measurements performed at least twice weekly until BP is ≤ ULN.
 - The algorithm below will be used to manage pazopanib related hypertension.
 - Hypertension should be managed with appropriate anti-hypertensive agent(s) as clinically indicated. It is strongly recommended that nephrology or cardiology be consulted in the evaluation and management of hypertension.
 - For patients who were on one anti-hypertensive medication at study enrollment and hypertension worsens while on study, further anti-hypertensive therapy may include dose adjustment of the current medication or the addition of a second anti-hypertensive medication.

Elevations in BP are based on systolic or diastolic pressures.

* Elevated blood pressure (BP) measurements should be repeated on the same day to confirm the elevation. Patients with elevated BP at any time should have BP measurements performed at least twice weekly until BP is within the ULN.

[§] ULN (Upper Limit of Normal) is a BP equal to the 95th percentile from age, height, and gender-appropriate normal values (Appendix VIII)

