If BP >25 mm Hg above ULN for age (verified) or Grade 4 HTN at any time, hold drug. Study drug should also be held for BP ≤ 25 mm Hg above the ULN age for > 14 days or 35 mmHg above baseline for > 14 days. Antihypertensive agents can be used to control hypertension as clinically indicated after study drug is held.

- Anti-hypertensive therapy should be prescribed as clinically indicated, including the use of multiple anti-hypertensive agents.
- # Baseline BP is defined in Section 5.4.

Arm 1 of algorithm:

• If blood pressure (BP) \leq 95% ile for age, height, and gender: continue pazopanib at the same dose.

Arm 2 of algorithm:

- If $BP \le 10 \text{ mm Hg}$ above the ULN: continue pazopanib at the same dose and recheck the BP within 72 hours.
 - If the BP is \leq ULN on recheck, continue pazopanib at the same dose.
 - $_{\odot}$ If the BP remains above the ULN on recheck, then start/adjust antihypertensive therapy (Section 4.1.5.1) and follow Arm 3 of the algorithm from the point that anti-hypertensive therapy is started/adjusted.

Arm 3 of algorithm:

- If BP is 11 to 25 mm Hg above the ULN on ≥ 2 of 3 measurements or > 35 mmHg above baseline on ≥ 2 of 3 measurements, start/adjust antihypertensive therapy (see Section 4.1.5.1) and continue pazopanib at the same dose. Monitor BP at least twice weekly.
 - If the BP returns to \leq ULN within 14 days, continue pazopanib at the same dose and continue anti-hypertensive therapy.
 - If the BP remains elevated ≥ 25 mm Hg above the ULN or > 35 mm Hg above baseline for more than 14 days after the institution/adjustment of anti-hypertensive therapy, **hold** pazopanib, monitor BP at least every 3 days, and follow Arm 4 of the algorithm from the point that pazopanib is held. The anti-hypertensive therapy should be continued until the BP is less than the ULN.
- If the BP returns to \leq ULN within 14 days, restart pazopanib at a reduced

dose.

- If the BP remains > ULN for more than 14 days, patient must be removed from protocol therapy.
 - If the BP increases to > 25 mm Hg above the ULN despite antihypertensive therapy, **hold** pazopanib, but continue the anti-hypertensive agent(s). Monitor the BP as clinically indicated and follow Arm 4 of the algorithm from the point that pazopanib is held.
- If the BP is ≤ ULN within 14 days, pazopanib may be restarted at a reduced dose.
- If the BP is > ULN for > 14 days, the patient must be removed from protocol therapy (Section 8.1).

Arm 4 of algorithm:

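### Protocol 5.4.1, Arm 3: the 14-day hold threshold of ≥ 25 mm Hg above the ULN is very probably a slip for ≤ 25, and leaves Arm 3 with no instruction for persistent smaller elevations

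*Protocol*

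**What the plan says.** Protocol 5.4.1 manages pazopanib-related hypertension through a note and five arms. The ULN is the 95th percentile for age, height and gender (140/90 from age 18). Systolic and diastolic pressure both count: an elevation in either the systolic or "diastolic blood pressure should be considered when following the algorithm below".

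- **Note before the arms.** Hold at any time for a verified pressure more than 25 mm Hg above the ULN or for Grade 4 hypertension. It adds: "Study drug should also be held for BP ≤ 25 mm Hg above the ULN age for > 14 days", or for 35 mm Hg above baseline over the same period.
- **Arm 2** (up to 10 mm Hg above the ULN). If the recheck is still above the ULN, start or adjust treatment and "follow Arm 3 of the algorithm from the point that anti-hypertensive therapy is started/adjusted".
- **Arm 3, entry.** "If BP is 11 to 25 mm Hg above the ULN on ≥ 2 of 3 measurements", or more than 35 mm Hg above baseline on the same count of readings.
- **Arm 3, back to or below the ULN within 14 days.** "continue pazopanib at the same dose and continue anti-hypertensive therapy".
- **Arm 3, 14-day hold.** "If the BP remains elevated ≥ 25 mm Hg above the ULN or > 35 mm Hg above baseline for more than 14 days" after treatment was started or adjusted: hold.
- **Arm 3, worsening.** "If the BP increases to > 25 mm Hg above the ULN despite antihypertensive therapy": hold, with no waiting period.
- **Arm 3, after a hold.** Restart at a reduced dose if the pressure returns to the ULN or below within 14 days. Otherwise: "If the BP remains > ULN for more than 14 days, patient must be removed from protocol therapy".

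Protocol 5.1.2.5 makes a pressure 1–25 mm Hg above the 95th percentile for more than 14 days dose-limiting in patients already on anti-hypertensives for previous hypertension.

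**The concern.** Arm 3 receives patients at 11–25 mm Hg above the ULN, at up to 10 mm Hg through Arm 2, or at more than 35 mm Hg above baseline. Its 14-day hold should say what to do when treatment has not worked for them. As printed, the ULN part starts at the very top of that range, where the immediate hold is about to take over. The note gives the same number, duration and action with the sign reversed.

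This is a dose-hold threshold in a paediatric safety rule. A site using the step-by-step arm as its working instruction could keep a child on full dose, above the 95th percentile, after more than 14 days of anti-hypertensives, when the note requires a hold.

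**Working it through.** No sample-size or power figure is involved. The check is which pressures receive an instruction from Arm 3.

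**Inputs.** The thresholds come from Protocol 5.4.1. Let d be mm Hg above the ULN, in whole units, persisting for more than 14 days on treatment. Let g be ULN minus baseline. The documents do not give g, so it is varied as an assumption.

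**Arm 3 as printed (≥ 25):**
- d ≤ 0: continue
- d ≥ 25, or d + g > 35: hold after 14 days
- d > 25: hold at once

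The immediate hold already takes every d > 25, so the ULN part of the 14-day rule contributes only d = 25. Arm 3 gives no instruction where 1 ≤ d ≤ min(24, 35 − g).

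| g (mm Hg) | No Arm 3 instruction, ≥ 25 as printed | No Arm 3 instruction, ≤ 25 |
|---|---|---|
| 0, 5, 10 | d = 1–24 | none |
| 15 | d = 1–20 | none |
| 20 | d = 1–15 | none |
| 25 | d = 1–10 | none |
| 30 | d = 1–5 | none |

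With ≤ 25, values 1–25 are held after 14 days and values above 25 at once, so nothing above the ULN is left out.

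**In actual pressures.** For a boy aged 10 at the 50th height percentile, Appendix V gives a ULN of 119/80. The baselines below are assumed.

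| Baseline | g (systolic, diastolic) | Systolic range without instruction | Diastolic range without instruction |
|---|---|---|---|
| 108/69 | 11, 11 | 120–143 | 81–104 |
| 105/60 | 14, 20 | 120–140 | 81–95 |
| 95/50 | 24, 30 | 120–130 | 81–85 |
| 84/45 | 35, 35 | none | none |

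A child falls in the gap only if neither pressure meets an Arm 3 hold criterion.

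**Which sign fits the rest of the text.**
- The note holds at ≤ 25 for more than 14 days. This is the most direct evidence.
- Arm 3's only 14-day outcome that continues dosing is a pressure at or below the ULN.
- Once drug is held, a pressure still above the ULN after 14 days means removal. As printed, a child held at 25 who falls to 1 mm Hg above the ULN and stays there is removed, while a child on full dose at 24 above gets no Arm 3 instruction.
- The 1–25 band in 5.1.2.5 agrees with ≤ 25, but only as support, because it is limited to patients already treated for previous hypertension. Protocol 5.3.1(b) sends pazopanib-specific toxicities back to 5.4, so it does not settle the matter.

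**How often the algorithm might be used.** Protocol 2.4.2 reports drug-related hypertension in 13 phase I patients against 27 normotensive: 13/(13 + 27) = 32.5%, exact 95% CI 18.6–49.1%. This is a rough guide to use of the algorithm, not a count of children in the gap.

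**The case against.** The strongest objection is that everything turns on one character in machine-read text. The Arm 3 bullet appears only once, the flowchart is not reproduced in the text reviewed, and inequality signs elsewhere are not captured consistently. A misread symbol cannot be excluded. This stands, and it is why checking the source comes first and confidence is medium.

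Second, the note already requires the hold and is not limited to any arm, so both texts can be obeyed together. That is correct. The claim is only that Arm 3 is silent; nothing in it authorises continuing. The harm needs a site that works from the arm without the note.

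Third, the removal rule for a pressure still above the ULN after 14 days might be read as covering the 1–24 range, because its indentation places it at the outer level of Arm 3. It follows the instruction to restart at a reduced dose, so it belongs to the period after a hold and does not fill the gap.

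Fourth, these children are still managed: pressure is checked at least twice weekly, specialist consultation is strongly recommended, several agents may be used, more than 25 mm Hg is held at once, and Grade 4 leads to removal. These safeguards limit the harm but do not supply the missing 14-day instruction.

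Finally, SAP 4.3 records that the study was declared futile after stage 1 and that termination was approved. This reduces the practical reach to any patient still on drug and to re-use of the algorithm elsewhere.

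**Conclusion.** The concern holds, with medium confidence. Taken as printed, the Arm 3 threshold is wrong: its ULN part adds a hold at one value only, and it leaves 1 to min(24, 35 − g) mm Hg above the ULN without an Arm 3 instruction after 14 days of treatment. Reading ≥ as a slip for ≤ reconciles Arm 3 with the note and with the 1–25 band in 5.1.2.5, and removes the gap at every baseline. The conclusion assumes that the symbol was read correctly and that the missing flowchart does not already resolve it. The documents do not show how many children stay 1–24 mm Hg above the ULN for 14 days, so the number affected is unknown. This should be fixed because it is a dose-hold rule.

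**What to change.** First confirm the symbol in the source document and the flowchart. The shared cooperative-group hypertension guideline mentioned in Protocol 2.4.2 is a further check.

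Then reword the Arm 3 bullet along these lines: *hold pazopanib if, more than 14 days after anti-hypertensive treatment was started or adjusted, BP is still above the ULN by up to 25 mm Hg, or is more than 35 mm Hg above baseline.* Stating that the pressure is still above the ULN matters, because ≤ 25 alone would literally include normal values. Give the note the same thresholds and the same start point for its 14 days: it now has no start point and omits the greater-than sign before 35 mm Hg. Section 5.1.2.5 needs no change.

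The cost is one symbol, matching wording in the note, and a short clarification to any site with a patient still on drug. No new assessments are needed. The downside is that sites that had been using Arm 3 alone will hold, reduce or stop treatment in some patients they would have kept on full dose.

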2.5 Overview of Proposed Pediatric Phase II Trial

This is a two-stage open label phase II trial of pazopanib in children, adolescents and young adults with recurrent or refractory solid tumors. Tumors of primary interest are rhabdomyosarcoma, non-rhabdomyosarcomatous soft tissue sarcoma (including synovial sarcoma, alveolar soft part sarcoma and desmoplastic small round cell tumor) and Ewing sarcoma/peripheral PNET. Tumors of secondary interest include hepatoblastoma, neuroblastoma (measurable and evaluable), and osteosarcoma.

Each tumor type defines a cohort resulting in 7 total cohorts. The first stage of the study involves enrolling an initial 10 patients into each cohort. The response rate will be determined for each cohort after the target enrollment of 10 patients is reached for that cohort. If one or more confirmed responses are observed in the first 10 evaluable patients in a cohort, an additional 10 patients will be enrolled into that cohort in the second stage of study. Thus, for cohort(s) with one or more confirmed responses in the first stage of study, a total of 20 patients will be enrolled and evaluated to determine efficacy.

Eligible patients will receive pazopanib monotherapy. Pazopanib will be dosed daily as an oral tablet (450 mg/m²/dose, maximum 800 mg) or as a powder for oral suspension (225 mg/m²/dose, maximum 400 mg) in 28 day cycles.

The MTD for pazopanib tablets was 450 mg/m²/dose as determined by ADVL0815/PZP114411, the COG Phase I study in children with relapsed or refractory solid tumors. For the powder suspension formulation, the selected starting dose is higher than the protocol-defined MTD of 160 mg/m²/dose established in ADVL0815. This decision is driven by the considerations that the 160

isolated and reversible laboratory-defined DLTs were observed at the 225 mg/m²/dose.

The first patients who are enrolled to receive pazopanib as powder suspension at 225 mg/m²/dose daily will be closely monitored for safety and for the occurrence of dose-limiting toxicity during the first cycle (28 days) of therapy. Patients who either receive 225 mg/m²/dose daily for at least 24 days (85% of the dose for a 28-day cycle with powder suspension at 225 mg/m²/dose) or are withdrawn from dosing due to one or more protocol-defined dose-limiting toxicities (Section 5.1) during the first cycle will be considered evaluable for the purpose of this safety review. Six evaluable patients are required.

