5.1 Definition of Dose Limiting Toxicity (DLT)

DLT will be defined as any of the following events that are at least possibly, probably, or definitely attributable to pazopanib. See Section 5.4 for the Potential Pazopanib Specific Side Effects. Dose-limiting hematological and non-hematological toxicities are defined differently.

5.1.1 Hematological Dose-Limiting Toxicity

- a) For patients who are evaluable for hematologic toxicity assessment (patients **without** bone marrow involvement)
 - Grade 4 Thrombocytopenia (platelet count < 25,000/mm3) or Grade 4 neutropenia
 - Any hematologic toxicity requiring dose reduction or treatment interruption for >14 days

b) For all patients:

- \geq Grade 2 arterial thromboembolic events (visceral arterial ischemia, peripheral ischemia, or ischemia cerebrovascular)
- Grade 3 or 4 venous thromboembolic event
- Any thrombotic event (other than central venous line [CVL] associated thrombosis) requiring systemic anticoagulation

5.1.2 Non-Hematological Dose-Limiting Toxicity

- 5.1.2.1 Any Grade 4 non-hematologic toxicity
- 5.1.2.2 Any Grade 3 non-hematological toxicity, with the specific exclusion of the following:
 - Grade 3 nausea and vomiting of less < 3 days duration
 - Grade 3 fever or infection,
 - Grade 3 hypophosphatemia, hypokalemia, hypocalcemia or hypomagnesemia responsive to oral supplementation within 7 days of start of supplement (see Section 5.4.4 for dose modifications)
- 5.1.2.3 Grade 2 allergic reactions that necessitate discontinuation of protocol therapy will not be considered a dose-limiting toxicity.
- 5.1.2.4 Any Grade 2 non-hematological toxicity that persists for \geq 7 days and is considered sufficiently medically significant or sufficiently intolerable by patients that it requires treatment interruption may also be considered a DLT following discussion with the Study chair and a Novartis Medical Lead.
- 5.1.2.5 Hypertension will be graded according to the NCI CTCAE; however, dose limiting hypertension will be considered as the following:

- Grade 4 hypertension
- A blood pressure >25 mmHg above the 95th percentile for age, height, and gender (see Appendix V) confirmed by repeated measurement on the same day (See Sections 5.4.1 and 4.1.5.1 for management)

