5.3 Dose Modifications for Non-Hematological Toxicity

Specific instructions for the management of potential pazopanib side effects are included in Section 5.4.

- 5.3.1 For any non-hematologic dose limiting toxicity as detailed in Section 5.1.2:
 - a) Pazopanib should be held
 - b) If the non-hematologic DLT is a pazopanib specific toxicity, the dosing guidelines in Section 5.4 should be followed
 - c) If the non-hematologic DLT returns to baseline within 14 days of holding pazopanib, subsequent doses of pazopanib should be given at a reduced dose.
 - If toxicity does not resolve to meet continued treatment parameters within 14 days of drug discontinuation, and if re-challenge is to be considered, the Study Chair must be contacted as outlined in Section 4.2 to discuss.
 - If DLT recurs in a patient who has resumed treatment after the maximum allowed dose reductions, the patient must be removed from protocol therapy, unless the patient has been approved for a further dose reduction following discussion with the Study Chair.

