		 daily If on 600 mg, then reduce to 400 mg daily If on 400 mg, reduce to 200 mg daily For patients on powder suspension: Follow the sequential dose reduction (Section 4.1.1.), one dose level reduction
	6.	is required (e.g. from 225 mg/m2 to 160 mg/m2) Following re-introduction of pazopanib, continue
		to monitor ALT weekly for 2 cycles, if $ALT \ge$ Grade 2 recurs permanently discontinue pazopanib

-
Liver Event Stopping Criteria ³ :
1. Discontinue pazopanib permanently
2. Recheck LFT's', serum creatinine
phosphokinase (CPK) and collect PK sample. Also check:
 Eosinophil count Optional viral serology⁴ for hepatitis A, B, C and E, cytomegalovirus⁴, Epstein- Barr virus⁴ (IgM antibody, heterophile antibody, or monospot testing) Anti-nuclear antibody⁴, anti-smooth muscle antibody⁴, anti-mitochondrial antibody⁴ Liver imaging (Ultrasound) Recommend referral to (consult) a pediatric gastroenterologist/hepatologist. Monitor patient closely for clinical signs and symptoms. Perform full panel LFTs¹ weekly or more frequently if clinically indicated until LFTs are reduced to Grade 1
 Isolated hyperbilirubinemia (in the absence of elevated ALT or other signs/symptoms of liver injury) does not require dose modification. Study treatment inhibits UGT1A1 and OATP1B1, which can cause elevation of indirect (unconjugated) bilirubin in the absence of liver injury If total bilirubin is >1.5 ULN in the absence of ALT elevation, fractionation of bilirubin should be performed. If the bilirubin is predominantly indirect (≥65%) indirect (unconjugated), continue study treatment at the same dose. If bilirubin is >35% direct (conjugated), study treatment may also be continued however, further evaluation should be undertaken for underlying cause of

¹LFTs include: AST, ALT, alkaline phosphatase, GGT and total bilirubin.

²Serum bilirubin fractionation should be performed if testing is available. If testing is unavailable and a patient meets the criterion of total bilirubin > 1.5 x ULN, then the event should be promptly reported as defined. ³When a liver chemistry event meets the Liver Event Interruption Criteria, or Liver Event Stopping Criteria, blood samples should be obtained for clinical laboratory testing by the central laboratory (Liver Event Kits will be provided for this purpose).

⁴These extra tests will be performed centrally

5.4.4 Electrolyte Abnormalities:

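### An attributable isolated Grade 3 or higher bilirubin rise counts as a DLT toward the 2-of-6 suspension rule, although Protocol 5.4.3 says it needs no dose change.

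*Protocol*

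**What the plan says.** **Definition.** Protocol 5.1 sets the attribution condition: "DLT will be defined as any of the following events that are at least possibly, probably, or definitely attributable to pazopanib". Under 5.1.2.1 the Grade 4 limb is "Any Grade 4 non-hematologic toxicity", with no exception. The Grade 3 limb, 5.1.2.2, begins "Any Grade 3 non-hematological toxicity, with the specific" and goes on to exclude three things: short-lived nausea and vomiting, fever or infection, and four electrolyte deficits that respond to oral supplements. Bilirubin is not among them.

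**Management.** The isolated-bilirubin row of 5.4.3 says: "Isolated hyperbilirubinemia (in the absence of elevated ALT or other signs/symptoms of liver injury) does not require dose modification". It gives a drug mechanism: "Study treatment inhibits UGT1A1 and OATP1B1, which can cause elevation of indirect (unconjugated) bilirubin in the absence of liver injury". Above 1.5 × ULN the bilirubin is to be fractionated. If it is mainly indirect, treatment goes on at the same dose. If more than 35% is direct, treatment may still go on, but the cause must be looked into. The available text of the row sets no upper grade.

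**General rule for non-hematologic DLTs.** Section 5.3.1 applies "For any non-hematologic dose limiting toxicity as detailed in Section 5.1.2". Item (a) reads "Pazopanib should be held". Item (b) refers pazopanib-specific toxicities to 5.4. Item (c) provides for a reduced dose after recovery.

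**Dose decision.** Under 2.5 the first patients on the 225 mg/m² suspension "will be closely monitored for safety and for the occurrence of dose-limiting toxicity during the first cycle (28 days) of therapy". Two or more DLT patients among 6 evaluable ones stop enrollment at 225 mg/m², and later patients start at 160 mg/m² (also 4.1 and 7.3.2). A patient is evaluable after at least 24 days at 225 mg/m², or if withdrawn from dosing because of a Section 5.1 DLT.

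**The concern.** The same laboratory event is dose-limiting in one section and needs no dose change in another. The 2-of-6 rule counts Section 5.1 DLTs without a bilirubin exception. The 225 mg/m² suspension dose could therefore be declared not tolerated partly or wholly on events for which the protocol leaves the individual child's dose unchanged. The alternative starting dose, 160 mg/m², is one that 4.1 itself describes as possibly giving too little exposure to show efficacy.

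Elsewhere the protocol ties the two together: the electrolyte exclusion in 5.1.2.2 points to 5.4.4, and hypertension has its own DLT wording in 5.1.2.5 with a pointer to 5.4.1. Isolated bilirubin has a management row but no matching DLT wording.

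**Working it through.** **1. Is the event a DLT?** If it is Grade 3 or 4 and judged at least possibly attributable, yes under 5.1.2.1 or 5.1.2.2, because no exclusion applies. Attribution is decided case by case (11.6.2). The mechanism named in 5.4.3 makes it easy to meet for indirect bilirubin; it does not cover a mainly direct rise.

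**2. Does it count?** Yes. Sections 2.5 and 7.3.2 tie the 2-of-6 rule to Section 5.1, and 4.1 repeats the threshold without an exception.

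**3. What happens to the patient's dose?** Read alone, 5.3.1(a) means hold. Through 5.3.1(b), 5.4.3 means no dose change. Nothing says expressly that (b) displaces (a).

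**4. Does the choice affect the denominator?** A 28-day cycle with at least 24 days required leaves 28 − 24 = 4 days to spare. A patient who continues under 5.4.3 can reach 24 days, is evaluable and is counted. A patient held for more than 4 days, or held and restarted at a reduced dose before completing 24 days at 225 mg/m², misses 24 days and is not plainly withdrawn from dosing. That patient may be non-evaluable. The two readings can thus give different six-patient reviews from the same event.

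**5. How large could the effect be?** The plan states no operating characteristic for the 2-of-6 rule, so there is no figure to reproduce. Inputs:

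- n = 6 and threshold 2 (Protocol 2.5, 4.1).
- p = first-cycle rate of all other DLTs: not in the documents, assumed 5% to 30%.
- q = rate of attributable isolated Grade 3 or higher bilirubin rises: not in the documents, assumed 2% to 10%, independent of the other DLTs.

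Formulae: u = 1 − (1 − p)(1 − q), and P(halt) = 1 − (1 − u)^6 − 6u(1 − u)^5. When the bilirubin events do not count, u = p.

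For p = 0.10:

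- Not counted: 1 − 0.9^6 − 6 × 0.1 × 0.9^5 = 1 − 0.5314 − 0.3543 = 0.114.
- q = 0.02: u = 1 − 0.90 × 0.98 = 0.118, P = 0.151.
- q = 0.05: u = 1 − 0.90 × 0.95 = 0.145, P = 0.212.
- q = 0.10: u = 1 − 0.90 × 0.90 = 0.190, P = 0.320.

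| Other DLTs (p) | Not counted | q = 2% | q = 5% | q = 10% |
|---|---|---|---|---|
| 5% | 0.033 | 0.059 | 0.109 | 0.212 |
| 10% | 0.114 | 0.151 | 0.212 | 0.320 |
| 20% | 0.345 | 0.384 | 0.442 | 0.536 |
| 30% | 0.580 | 0.610 | 0.652 | 0.717 |

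The difference between a counted and a not-counted cell is the chance that bilirubin events decide the outcome. In this table it is 0.03 to 0.04 at q = 2%, 0.07 to 0.10 at q = 5%, and 0.14 to 0.21 at q = 10%. Two isolated bilirubin events with no other DLT would be enough; the chance that at least 2 of 6 patients have one is 0.006, 0.033 or 0.114 at q = 2%, 5% or 10%.

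**The case against.** The best case for the plan is that it already gives an answer. Section 5.1 defines the DLT, 2.5 refers to 5.1, and so the event counts; whether it ought to count is a design choice. Section 5.3 opens by pointing to 5.4 for pazopanib side effects and 5.3.1(b) repeats it, so the specific text should govern the dose. Much of this stands, and it rules out several stronger readings that a reader might infer:

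- **That the patient must be held.** Section 5.3.1(b) makes this unlikely; only the missing order between (a) and (b) remains.
- **That the event calls for no action.** Section 5.4.3 requires fractionation and, for a mainly direct rise as the row defines it, further evaluation. Only the dose is left alone.
- **That the DLT count is undefined.** As written, the event counts.
- **That admitting Gilbert's syndrome makes such events likely.** Section 3.2.8.3(d) exempts it only from the bar on active liver or biliary disease; 3.2.8.3(a) still caps total bilirubin at 1.5 × ULN.

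The rates are also open to challenge. The phase I summary in 2.4.1 covers 51 eligible patients and names no bilirubin DLT. If that meant 0 of 51, the one-sided 95% upper bound would be 1 − 0.05^(1/51) = 5.7%, which makes 10% look high. The list may be incomplete, the evaluable number is not given, and doses and formulations are mixed, so this is only a guide. It does favor the lower columns of the table.

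Finally, SAP 4.1 has the team review the toxicity profile of the first six suspension patients, SAP 11.2 lists DLTs individually, and SAP 4.3 records that the study was declared futile and its termination approved after Stage 1. The practical value now lies mainly in reporting. None of this removes the mismatch between 5.1.2 and 5.4.3 or the evaluability problem in step 4.

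**Conclusion.** The concern holds in a limited form. An event that the protocol says needs no dose change is, as written, a DLT that can help move new suspension patients from 225 to 160 mg/m². The unstated order of 5.3.1(a) and (b) can change whether that patient is among the six.

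That logic follows from the text; its size does not. At p = 10% the chance of halting goes from 0.114 to 0.151, 0.212 or 0.320 for q of 2%, 5% or 10%. This assumes independent events, all judged attributable, in patients who remain evaluable. The documents give neither p nor q.

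A reader might also infer that the event should not be a DLT, or that the suspension dose was in fact decided this way. The documents support neither: they do not say which rule was intended, and they do not report whether any such event occurred.

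**What to change.** Reconcile Protocol 5.1.2, 5.3.1(a) and (b), the isolated-bilirubin row of 5.4.3 and the evaluability text in 2.5, so that this event has one stated DLT status, one dosing instruction and one evaluability outcome. Which status and which instruction is for the sponsor and the cooperative group to decide. The exclusion list in 5.1.2.2 should then agree with that decision.

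Whatever is decided, show isolated bilirubin events separately in the six-patient suspension review and in the SAP 11.2 DLT summary, so that a reader can see the count with and without them. If the protocol is no longer being amended, the separate display in the clinical study report can still be made.

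The cost is a few lines of protocol text and one extra row in the DLT summary. No additional patients or data are needed.
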